2. OBJECTIVES

Objective

This study intends to deliver the “proof-of-concept” that locally administered pilocarpine drops in two doses are effective in a population of elderly (aged ≥ 70 years) with xerostomia at the expense of limited adverse events. To this end, the study aims to quantify the effect size of pilocarpine in two different dosages. In case we observe clinically meaningful changes in xerostomia through measured NRS, a sufficiently-powered RCT will be prepared to compare pilocarpine to placebo.

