6.6 Dosages, dosage modifications and method of administration

The two doses pilocarpine nitrate (3 x 2.0 mg = 3 x 2 drops or 3 x 5.0 mg = 3 x 5 drops) will be stable over the first 14 days of the study. Day 15 through day 21 patients will not receive medication. Drops will be administered left and right outside the molars and behind the front teeth under.

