8.1.2 Secondary study parameters/endpoints

- Adverse effects
- Other symptoms
- Global perceived effect

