8.3 Study procedures

The study will be performed at the outpatient clinic internal medicine/elderly care of the Maastricht University Medical Centre+. Potentially eligible patients will be identified on the outpatient clinic by answering the question if they have suffered from a dry mouth in the last three months. If the answer to this question is yes they will be invited to participate when meeting the inclusion criteria.

Each patient that participates in this study will receive a restaurant coupon and their travel expenses will be covered.

Randomisation will occur through a sealed envelope system. Once a patient has consented to the trial, a sealed opaque envelope is opened and the patient will receive the allocated treatment regime. This sealed opaque envelope will also contain a two digit number wherein the patient will be identified from this point forward in the database. The sealed opaque envelopes with all its content will be arranged by the researcher before start of the study.

Measures will be performed on day 0, 7, 14 and 21. Questionnaires on day 0, 7, 14 and 21, whole resting salivary flow on day 0 and 14, blood pressure will be measured on day 0 before and 1 hour after pilocarpine administration and on day 14.

	Day 0	Day 7	Day 14	Day 21
Hospital visit	X		X	
Patient characteristics	X			
Xerostomia NRS / GOHAI-NL	X	X	X	X
USD	X	X	X	X
EQ5D	X	X	X	X
GPE	X	X	X	X
Side effects	X	X	X	X
RR	X		X	
Whole resting saliva	X		X	

After inclusion the patient will visit the outpatient clinic twice on day 0 and day 14. On the first visit (day 0) after inclusion a questionnaire consisting of 45 questions, will be filled in, this will take 20 minutes. Also patient characteristics, including use of medication, will be accessed. Blood pressure and whole resting saliva will be measured. The blood pressure will be measured in sitting position using the Dinamap technology V100 care scape from general electric. The whole resting saliva will be measured by the doctor/research nurse. The patient will have to sit straight in a chair and will be asked to swallow the saliva that is currently in their mouth, in the next five minutes the patient will be asked to accumulate all the saliva that is spontaneously produced in their mouth. This whole resting saliva will be collected in a previously weighted cup and the result of each patient will be compared. The cups and the whole resting saliva will be measured with the SARTORIUS AC210p scale.

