On day 14 all of these procedures but one (assessment of patient characteristic) will be repeated. On day 7 and day 21 the patient will receive a phone call wherein the questionnaires will be taken by the doctor/research nurse. At the end of the study patients will be offered to continue the pilocarpine drops as off-label use. The reimbursement status for this indication is uncertain.

Table 1: Description of study procedures

	Procedure	Parameter	Description
Measurements	Whole resting saliva	Amount of saliva collected in 5 minutes	This procedure will be done twice during the study
	Blood pressure	mmHg	The sitting blood pressure will be measured using the Dinamap technology V100 care scape from general electric.
Questionnaires	0-10 Numeric Rating Scale (NRS)	Xerostomia	The NRS is used to quantify the level of severity of xerostomia using a 0-10 cm NRS ranging from 0 = no dry mouth to 10 = worst possible dry mouth.[28]
	Geriatric Oral Health Assessment Index (GOHAI-NL)	Xerostomia	Oral health-related quality of life (OHRQoL) of adults, in particular older people is measured 4 times during this study by the doctor/research nurse . It comprises of 12 items that measure three dimensions of OHRQoL: physical function items, psychosocial function and pain/discomfort. [33]
	Utrecht symptom Diary (USD)	concurrent symptoms	The USD asks patients to self-asses eleven symptoms and their wellbeing on a daily basis, by using a numerical rating scale ranging from 0 to 10. Patients can also indicate which symptom is a priority for them.[34, 35]
	EuroQoL 5D (EQ5D)	generic Health-Related Quality of Life (HRQoL)	Health-related quality of life is measured 4 times during this study by the doctor/research nurse, using five dimensions: mobility, self-care, usual activities, pain/discomfort and anxiety/depression.[36]

	Global Perceived Effect (GPE 7-point scale)	Global Perceived Effect (GPE)	The GPE scale asks the patient to rate, on a numerical scale, how much their condition has improved or deteriorated since some predefined time point.[37]
	4-point Likert scale	Side effects	Patients are asked if they experienced flu-like symptoms, sweating, headache, urinary frequency, diarrhoea, nausea, vomiting, palpitations, dizziness, rhinitis, or other symptoms, while on the treatment.

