10. STATISTICAL ANALYSIS

Primary and secondary study parameter(s)

Baseline characteristics will be described in detail per group in order to assess any imbalance. In case of missing data, we will use stochastic regression imputation to produce a synthetic part of the data to allow for an intention to treat analysis.

Per group, the post-treatment xerostomia score will be described as mean and standard deviation, or median and interquartile range in case of severe skewness. Additionally, we will compute a change-from-baseline score for both groups, which will be described in a similar matter. All secondary

outcome measures will be described in full using either mean and standard deviation or median and interquartile range for continuous measures, and count and proportion for categorical measures. For exploratory purposes, we will use the independent-samples t-test to test for differences in xerostomia complaint scores (NRS) between the two groups. However, as this is a pilot study, the emphasis will lie on clinical interpretation of the effect sizes of both groups separately. Preliminary analyses on secondary outcome measures will be performed using the independent samples t-test and Fisher's Exact test, depending on the measurement level of each variable.

Other study parameters

Not applicable.

Interim analysis

No interim analysis will be performed.

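### The side-effect checklist asks about symptoms during treatment but is given on day 0 and after the drug-free week, so side effects have no secure baseline

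*Protocol*

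**What the plan says.** - **Objective.** Protocol section 2 wants the drops shown to be effective "at the expense of limited adverse events". Section 8.1.2 lists "Adverse effects" as a secondary endpoint.
- **Wording of the item.** Table 1 in section 8.3 describes a 4-point Likert item on ten named symptoms (among them headache, urinary frequency, palpitations, dizziness and rhinitis), "or other symptoms, while on the treatment".
- **Timing.** Section 8.3 has "Questionnaires on day 0, 7, 14 and 21", and the schedule table marks side effects at all four. Section 6.6 says "Day 15 through day 21 patients will not receive medication".
- **Day 0.** A dose is given that day. Only blood pressure is timed around it: "blood pressure will be measured on day 0 before and 1 hour after pilocarpine administration and on day 14". The questionnaire is not.
- **Analysis.** Section 10 summarises secondary outcomes by mean or median if continuous and by "count and proportion for categorical measures", and compares the doses by t-test or Fisher's exact test. The sentence "Additionally, we will compute a change-from-baseline score for both groups" follows directly on the xerostomia score. No such statement is made for side effects. Interpretation is to rest mainly on each group taken on its own.

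**The concern.** The listed symptoms can occur in older patients on several medicines without any pilocarpine, and the protocol itself notes that polypharmacy is common at this age. To read one arm's rate as tolerability of that dose, the background has to be taken off. There is no placebo arm to supply it. The day 0 form could, and day 21 could show whether symptoms went away off the drug. The recall window weakens both: it cannot sensibly be answered before treatment, and after the drug-free week it has two possible meanings. This is a fault in data collection. If patients answer an ill-fitting question, no later analysis rule recovers a clean baseline.

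**Working it through.** The plan states no figure on this point, so there is none to reproduce. The check is mainly textual, with an illustration of size.

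**1. Window against schedule**

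| Assessment | Drug status | What the window covers |
|---|---|---|
| Day 0 | Treatment starting; form not placed before or after the first dose | Nothing, or the time since the first dose |
| Day 7 | On drug | Days 0 to 7 |
| Day 14 | End of the 14-day course | Read literally, days 0 to 14 |
| Day 21 | Off drug since day 15 | Days 0 to 14 again, or the past week; unclear |

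The wording fits two of the four assessments, and literally read those two cover periods of different length.

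**2. Link to day 0.** Section 10 ties change from baseline to the xerostomia score and gives no rule relating later side-effect reports to day 0. The adverse event definition in section 9.2.1 does not separate them either, since it includes events regardless of relation to the drug.

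**3. Size for one symptom, as an illustration.** Let b be the background rate and d the drug-related rate, acting independently. The observed rate is b + (1 − b)d, the rate among patients without the symptom on day 0 contributes (1 − b)d, and the background share is b divided by the observed rate. For d, take the 17% that section 1 gives for dizziness under systemic pilocarpine; this is not a rate for the drops. The documents give no b, so it is assumed. Each arm has 12 patients (section 4.4).

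| b (assumed) | Observed rate | Of 12 patients | New since day 0 | Background share |
|---|---|---|---|---|
| 0% | 17% | 2.0 | 17% | 0% |
| 5% | 21% | 2.5 | 16% | 24% |
| 10% | 25% | 3.0 | 15% | 40% |
| 20% | 34% | 4.0 | 14% | 60% |
| 30% | 42% | 5.0 | 12% | 72% |

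At b = 10%: 0.10 + 0.90 × 0.17 = 0.253, and 0.10 / 0.253 = 0.40.

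**4. Effect on the dose comparison.** With the same b in both arms, the observed difference is (1 − b) times the difference in drug-related rates, so its direction is kept. For assumed drug-related rates of 10% and 30% at b = 20%, the observed rates are 0.20 + 0.80 × 0.10 = 28% and 0.20 + 0.80 × 0.30 = 44%, a ratio of 1.6. The new-onset rates are 8% and 24%, a ratio of 3. The difference is 16 points either way.

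**5. How much a comparison with day 0 removes.** A persistent symptom is removed entirely. For an intermittent one, assume presence at each visit with probability 10%, independently across visits, and no drug effect. At a single visit, new reports run at 0.90 × 0.10 = 9% against 10% for all reports. If day 7 and day 14 are pooled, the chance of presence at either is 1 − 0.90² = 19%, and new reports are 0.90 × 0.19 = 17.1%. Over ten independent items, 1 − (1 − 0.171)^10 = 85% of patients would have at least one new item, against 1 − 0.81^10 = 88% for all reports. Pooling the two visits gives chance two opportunities against one baseline reading, so they should be shown separately.

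**The case against.** Several points on the other side stand.

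- **A reader might infer that symptoms present on day 0 will be counted as side effects.** No section says so. A day 0 form is collected, secondary outcomes are to be described fully, and tables by visit would show the day 0 level beside days 7 and 14. What the documents support is an unreliable baseline and no stated rule, not a plan to count background as harm.
- **A reader might infer that only counts will be reported.** The measurement level of the 4-point scale is not declared, so means or medians are equally allowed. They would carry the same background.
- **A reader might take the share of patients with at least one of the ten symptoms as the size of the error.** With no drug effect, 1 − (1 − p)^10 gives 18%, 40%, 65% and 89% at p = 2%, 5%, 10% and 20%. That is not a planned endpoint, and the figures rest wholly on assumed prevalences and independence; positive correlation lowers them.
- **Table 1 paraphrases the instruments.** The patient form is not shown and may be worded better. If so, Table 1 still has to be brought into line with it.
- **A treatment-emergent definition can sit in a statistical analysis plan.** That is true of the reporting rule, but not of the recall window or the timing of the day 0 form.
- **The stakes are limited.** The only stated trigger for a follow-on trial is the xerostomia rating, no tolerability threshold is set, and that trial would be against placebo. Co-morbidity and medication are recorded at inclusion, and the Utrecht symptom Diary is completed on day 0. The diary's eleven symptoms are not named in the protocol, so its overlap with the checklist cannot be established.

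**Conclusion.** The point holds as a mismatch between the recall window and the schedule, combined with no stated link from later reports to day 0. The first part is certain from the text of Table 1 as it stands. The second is a gap in section 10 that matters because tolerability is part of the objective, there is no placebo arm and each dose is read separately. The amount of background in the per-arm figures cannot be stated from the documents. In the illustration it runs from none to 72% of the observed rate, over assumed background rates of 0% to 30% and a borrowed 17% drug-related rate. The comparison between doses is not biased in direction, because randomisation balances background on average; at most it is attenuated. This is worth correcting before enrolment, because the wording and timing cannot be repaired afterwards.

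**What to change.** 1. In Table 1 and on the form, use one neutral recall window at every assessment, for example the past 7 days.
2. State in section 8.3 that the day 0 form is completed before the first dose.
3. In section 10, report each item per arm and per visit as all reports and, beside it, as new or worse than day 0. Show day 7 and day 14 separately, and use day 21 to describe resolution off drug.

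The cost is a wording change, a timing statement and one extra table, with no additional visits, patients or change to treatment. There are two downsides. Worsening from a maximal day 0 rating cannot be seen on the checklist, though it can still be recorded as an adverse event. Intermittent symptoms are only partly removed by the comparison with day 0, so the new-or-worse figures should not be read as purely drug-related.

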8.4 Withdrawal of individual subjects

Subjects can leave the study at any time for any reason if they wish to do so without any consequences. The investigator can decide to withdraw a subject from the study for urgent medical reasons.

8.4.1 Specific criteria for withdrawal

Unacceptable adverse effects.

8.5 Replacement of individual subjects after withdrawal

Individual subjects will not be replaced after withdrawal.

8.6 Follow-up of subjects withdrawn from treatment

Patients will receive usual care after withdrawal

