Current symptomatic treatment options include local treatment with artificial saliva/mouthwashes or systemic or local administration of pilocarpine. The former has mainly been researched in advanced cancer patients[12, 13] and was not better than chewing gum.[14] The latter are the current mainstay treatment of patients in the palliative phase of their illness.[12] Pilocarpine is a parasympathomimetic drug that increases saliva production by activating muscarinic receptors.[12] Pilocarpine tablets (systemic treatment) are more effective than placebo in radiation-induced xerostomia,[15-18] Sjögrens disease, [19] tramadol induced oral dryness[20] and improved salivation in patients taking xerogenic medications.[21] However, systemic administration of pilocarpine has frequent side-effects such as sweating (20 -50%), flushing, rhinitis (12%), headaches (12%), increased frequency of urination (11-34%), flu-like symptoms (8%), asthenia (7%)[21-23] and, mainly in elderly patients, dizziness (17%) leading to dropout rates between 6% and 15% in clinical studies.[16] Local oral administration of pilocarpine (drops, lozenges and mouthwashes) are reported to have none [24, 25] or minor local side effects (irritation of mouth and tongue).[26] In addition, a 5 mg pilocarpine lozenge produced better clinical results than a 5 mg pilocarpine tablet in 33 head-and-neck cancer

patients.[27], Furthermore, pilocarpine eye drops 2% relieved xerostomia immediately in 19 patients with opioid-induced complaints of dry mouth.[25] However, inconclusive results have been reported about the effectiveness of these local formulations in other studies.[24, 28].

Literature is scarce on the effectiveness of pilocarpine in elderly patients with xerostomia.

Pilocarpine mouthwash relieved dry mouth in 19 elderly patients[26], whereas a systematic review evaluating the effectiveness of systemic pilocarpine in 242 elderly patients with xerostomia due to medication or unknown causes showed inconclusive results.[1] As our population is ageing and poly-pharmacy is common among elderly, more patients will be poly-medicated in the future. Hence, xerostomia will be a major problem and thus more research on this topic is necessary.

This study intends to deliver the “proof-of-concept” that locally administered pilocarpine drops are effective in reducing xerostomia complaints in a population of elderly (aged ≥ 70 years) with xerostomia at the expense of a minimum of side effects.

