9.4 Follow-up of adverse events

All AEs will be followed until they have abated, or until a stable situation has been reached.

Depending on the event, follow up may require additional tests or medical procedures as indicated, and/or referral to the general physician or a medical specialist.

SAEs need to be reported till end of study within the Netherlands, as defined in the protocol

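### No side-effect checklist is provided for when a patient stops because of side effects, and the missing grades fall under a general imputation rule that would probably understate them

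*Protocol*

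**What the plan says.** - **Withdrawal.** Protocol 8.4.1 lists one specific criterion: "Unacceptable adverse effects". Under 8.5, "Individual subjects will not be replaced after withdrawal".
- **After withdrawal.** The whole of 8.6 reads: "Patients will receive usual care after withdrawal". It names no study assessment.
- **Timing.** Section 8.3 fixes "Questionnaires on day 0, 7, 14 and 21, whole resting salivary flow on day 0 and 14". The schedule has no assessment at the moment of stopping.
- **Instrument.** Side effects are graded on a 4-point scale. Patients are asked about flu-like symptoms, sweating, headache, "urinary frequency, diarrhoea, nausea, vomiting, palpitations, dizziness, rhinitis, or other symptoms, while on the treatment".
- **Missing data.** Section 10: "In case of missing data, we will use stochastic regression imputation to produce a synthetic part of the data". The stated purpose is an intention-to-treat analysis. No outcome and no reason for missingness is excepted.
- **Separate safety route.** Section 9.2.1 records adverse events that are reported spontaneously or observed, and 9.4 adds: "All AEs will be followed until they have abated, or until a stable situation has been reached".
- **Role of the outcome.** Adverse effects are a secondary endpoint (8.1.2), and limited adverse events are part of the objective (section 2).

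**The concern.** Withdrawal under 8.4.1 is triggered by the very outcome that the checklist measures. A patient who stops on day 3, for example, has no scheduled on-treatment checklist, and the section that should say what is still collected names only usual care. The gap is then closed with synthetic values. Stochastic regression imputation predicts a missing value from observed data and adds random scatter. It assumes that, given the predictors, patients with missing grades resemble those with observed grades. Here they do not, because the grade is missing since it was bad.

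At stake is the graded tolerability result for each dose, one of the things a pilot should hand on to the planned placebo-controlled trial. Section 6.3 says that side effects rise with dose, citing post-radiation oral studies. If that carries over to drops, the loss would fall more on the high-dose arm. An analysis plan can choose another imputation model, but it cannot recover grades that were never collected, so the matter belongs in the protocol.

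**Working it through.** **1. The plan's own figures.** The sample size is a rule of thumb, 2 x 12 = 24 (section 4.4), with no formula to reproduce. The protocol gives no withdrawal rate for the drops. Its only figure, in section 1, is for systemic pilocarpine: "dizziness (17%) leading to dropout rates between 6% and 15% in clinical studies".

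**2. How often might a patient be lost?** Assumption: the systemic range d = 6% to 15% applies to n = 12 per arm.

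- Expected number, n x d: 12 x 0.06 = 0.72 and 12 x 0.15 = 1.8 per arm; 24 x 0.06 = 1.44 and 24 x 0.15 = 3.6 in the trial.
- Chance of at least one, 1 - (1 - d)^n: 1 - 0.94^12 = 52% and 1 - 0.85^12 = 86% in one arm; 77% and 98% among all 24.

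These are chances of any dropout, not of withdrawal for an adverse effect before day 7, which is what the complete loss of on-treatment grades requires. They do not estimate how often the problem would arise.

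**3. How much does each lost patient matter?** Let w of 12 patients stop with a marked side effect and have no on-treatment checklist. Let q be the rate of marked side effects among the other 12 - w. If imputation gives the missing patients the completers' rate:

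- true rate = (w + (12 - w)q)/12
- expected rate after imputation = q
- understatement = w(1 - q)/12

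| w | q (assumed) | True rate | Expected after imputation | Understatement (points) |
|---|---|---|---|---|
| 1 | 0% | 8.3% | 0% | 8.3 |
| 1 | 10% | 17.5% | 10% | 7.5 |
| 1 | 20% | 26.7% | 20% | 6.7 |
| 1 | 30% | 35.8% | 30% | 5.8 |
| 2 | 0% | 16.7% | 0% | 16.7 |
| 2 | 10% | 25.0% | 10% | 15.0 |
| 2 | 20% | 33.3% | 20% | 13.3 |
| 2 | 30% | 41.7% | 30% | 11.7 |

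**4. Could a better imputation model avoid this?** Only in part. Treatment arm as a predictor does not separate those who stopped from those who stayed within an arm. Reason for withdrawal cannot help if nobody with that reason has an on-treatment grade, because there is nothing to estimate its effect from. An earlier on-treatment grade can help, but only for a patient who stops after day 7.

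**The case against.** The strongest reply is that the safety information is not lost. An investigator who withdraws a patient for adverse effects knows of the event; 9.2.1 requires it to be recorded and 9.4 to be followed. That stands, and it limits the point to the graded checklist. It does not remove the point: the 4-point checklist is the instrument the protocol assigns to side effects, and 9.2.1 asks for no matching grade.

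Two stronger readings are tempting, and the documents support neither.

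- A reader might infer that the worst-tolerating patients disappear from the side-effect result. They do not. Imputed patients stay in with synthetic values, and any checklist completed before withdrawal is kept.
- A reader might infer that 8.6 contradicts 9.4. It does not. Usual care describes treatment, and following an adverse event is a safety duty; both can be met for the same patient.

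Other objections stand in part. Section 8.6 does not say that measurement stops, so the absence of later checklists is inferred from silence, although this is the one section meant to define follow-up. The imputation sentence does not name side-effect grades; its reach follows from its general wording, and its predictors may be set in an analysis plan not seen here. The protocol also expects no or only minor side effects from local use, so such withdrawals may be rare.

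**Conclusion.** The point holds for the structured checklist, not for the adverse-event record. Followed as written, the protocol provides no checklist for a patient who stops because of side effects, and fills the missing grades by a method that treats them as predictable from observed patients. The probable direction is understatement: 5.8 to 8.3 percentage points for one such patient in an arm of 12, and 11.7 to 16.7 points for two.

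This rests on three assumptions: each such patient has a marked side effect and no on-treatment checklist, imputation centres on the completers' rate, and that rate lies between 0% and 30%. The frequency with drops is unknown and may be below the systemic range. A narrowed difference between doses is plausible but not shown, since it depends on how withdrawals split between the arms and on the imputation model.

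The change should be made but does not threaten the trial. Adverse effects are secondary, the comparisons between groups are exploratory or preliminary, and section 2 makes the step to the larger trial depend on the change in NRS.

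**What to change.** In 8.6, state that every patient who stops the drops completes the side-effect checklist at stopping and, unless consent is withdrawn, keeps the planned day-7, day-14 and day-21 questionnaires, by phone if preferred.

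In section 10, state that side-effect grades are not imputed, that these patients are classified by the grade recorded at stopping, and that withdrawals for adverse effects are reported as a count per arm.

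These changes concern data collection and reporting only; they leave the withdrawal criterion and care after withdrawal as they are. The cost is a few sentences and extra phone calls for about 1 to 4 patients in all if the systemic range applied (24 x 0.06 = 1.44 to 24 x 0.15 = 3.6). Some patients will decline further calls; the checklist at stopping then matters most.
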